#### 2.2.2 Secondary Outcomes

- 1) Change in haemoglobin levels between baseline and 3 months
- 2) Change in ferritin levels between baseline and 3 months
- 3) Number of eligible patients per site
- 4) Proportion of eligible patients agreeing to take part and passing screening
- 5) Feasibility of collecting proposed outcomes at baseline and 3 months for a future definitive trial:
  - Short physical performance battery (15)
  - Six-minute walk distance
  - Anaemia-related symptoms (e.g. breathlessness, tiredness, fatigue)
  - Health-related quality of life (EQ-5D-5L™, 15D©) (16, 17) (20)

- Activities of daily living (NEADL©) (18)
- Health care use including use of blood transfusions and hospitalisation
- All-cause mortality
- 6) Dropout rate at 3 months
- 7) Crossover rate at 3 months
- Change in functional limitation (six-minute walk <400m or short physical performance battery score ≤10) scores between baseline and 3 months
- Change in level of fatigue assessed using validated Fatigue Severity Scale (19) between baseline and 3 months
- 10) Change in medication adherence using Oral Iron Use Likert scale (in those taking oral iron only) between baseline and 3 months
- 11) Participant experience using semi-qualitative questionnaire at 3 months.

[figure not shown]
#### 3 STUDY DESIGN

#### 3.1 STUDY DESCRIPTION

Three-arm, parallel group, open-label (assessor blinded) pilot randomised controlled trial.

#### **STUDY FLOW CHART** 3.2

Abbreviations HB – Haemoglobin EQ5D5L: EuroQoL quality of life questionnaire

SPPB – Short physical performance battery 15D – health related quality of life questionnaire

FSS – Fatigue Severity Score NEADL: Nottingham extended activities of daily living questionnaire.

^

#### Table 4: Study Matrix

	Visit 1	Visit 2	Visit 3	Visit 4
	Combined	Randomisation	IV iron	3 month visit
	screening and	and telephone	administration visit	(1/2) weaks)
	baseline visit	call (+1 to 4 days)	(within 2 weeks of	(+/- 3 weeks)
			randomisation)	
Informed consent	X	X	X	Х
Inclusion/Exclusion Criteria	Х			
Demographics and medical	Х			
history				
Adverse Events Recorded		Х		Х
Height and weight	Х			
Medications	Х			Х
Oral Iron Use Scale	Х			X¶
Haemoglobin	Х			Х
Ferritin	Х			Х
C-reactive protein	Х			
Creatinine	X*			
eGFR	X*			
Short physical performance	Х			Х
battery				
Six-minute walk distance	Х			Х
Fatigue Severity Scale	Х			Х
Patient reported anaemia symptoms &	х			х
Quality of Life EQ-5D-5L & 15D	Х			Х
questionnaires				
Activities of Daily Living	Х			Х
(Nottingham EADL score)				
Health & Care Use	Х			Х
questionnaire				
Participants' experiences semi-				Х
qualitative questionnaire				
Randomisation (telephone call)		Х		
IV iron administration (if			Х	
required)				
Nutritional advice leaflet				Х

#### KEY

X Verbal consent check

\* Screening creatinine and eGFR sample results will be within 12 months of study entry; if this is not available use baseline creatinine and eGFR results to determine eligibility.

& Complete at the end of Month 1 & 2; return at Month 3 visit.

¶ Only participants randomised to continue oral iron – Telephone Call; unblinded RN.

#### 4 STUDY POPULATION

#### 4.1 NUMBER OF PARTICIPANTS

Community dwelling people aged 65 years or over who meet the following study eligibility criteria and reside within the catchment area of participating NHS organisations. A total of 84 participants (approximately 21 in each NHS site i.e. 7 participants randomised into each study arm) will be recruited into the study.

#### 4.2 INCLUSION CRITERIA

To be eligible, the participant will be assessed, and must meet all of the following criteria:

- 1. Provision of written informed consent
- 2. Community dwelling (i.e. not in hospital)
- 3. Age 65 years or over
- 4. Haemoglobin of >=85g/L and <=110g/L prior to commencing oral iron
- 5. Ferritin <100µg/L prior to commencing oral iron
- 6. Currently taking oral iron at any dose with a minimum of 8 weeks therapy
- Insufficient response to oral iron therapy (sufficient response defined as improvement in Hb of 20g/L after a minimum of 8 weeks of oral iron therapy or above lower limit of normal Hb level for sex)
- 8. Relevant investigations (including upper and lower GI endoscopies) either already conducted, offered but declined by the patient, or deemed not appropriate by the treating clinician. Only if applicable:
- 9. Oral iron therapy provided an initial sufficient response however Hb has now fallen below lower limit of normal for sex (Sufficient response is defined as an improvement in Hb of 20g/L or Hb above lower limit of normal for sex after a minimum of 8 weeks of oral iron therapy).

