#### S.2 SCIENTIFIC SUMMARY

Anaemia is a common problem, and is particularly common in older people. It is associated with fatigue, impaired functional capacity, increased hospitalization and mortality. In the USA, the prevalence of anaemia as defined by the World Health Organisation (Hb <130g/L in men and <120g/L in women) among community-dwelling adults age 65 years and older was 11.0% and 10.2% in men and women, respectively, rising to more than 20% in those >85 years.

In this pilot study we will recruit older people, aged 65 years or over, with mild-moderate iron deficiency anaemia (anaemia defined as haemoglobin (Hb) between 85 and 110 g/L and iron deficiency defined as ferritin <100µg/L prior to commencing oral iron) and who show insufficient response to oral iron therapy (sufficient response defined as improvement in Hb by 20g/L within 3 months of commencement of oral iron therapy) into a three-arm study. The study arms are:

- Treatment as usual
- Stop oral iron treatment
- Stop oral iron and give IV iron (as per local formulary).

The co-primary outcomes are:

- 1) the rate of randomisation per month across the pilot sites
- 2) the proportion recruited from each route of recruitment

Secondary outcomes are:

- 1) change in haemoglobin and ferritin levels at 3 months
- 2) number of eligible patients per site
- 3) proportion of eligible patients agreeing to take part and passing screening
- feasibility of collecting primary (physical functioning and health-related and general quality of life) and secondary outcomes for main trial:
  - Short physical performance battery
  - Six-minute walk distance
  - Anaemia-related symptoms (e.g. breathlessness, tiredness, fatigue)
  - Health-related quality of life (EQ-5D-5L™, 15D©)
  - Activities of daily living (NEADL©)
  - Health care use including use of blood transfusions and hospitalisation
  - All-cause mortality
- 5) dropout rate at 3 months; crossover rate at 3 months

- 6) reported side effects and adverse events (GI symptoms, headache, dizziness, rash)
- 7) functional limitation (six-minute walk <400m or short physical performance battery ≤10)
- 8) level of fatigue assessed using validated Fatigue Severity Scale
- 9) Patient experience.
- 10) Oral Iron Use Likert Scale (in those taking oral iron only)
- 11) Participant experience using semi-qualitative questionnaire.

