#### 5.5 RANDOMISATION

#### 5.5.1 Randomisation

After successful screening for eligibility and safety, and completion of baseline outcome measures, participants will be randomised on a 1:1:1 allocation ratio via a web-based system TRuST, run by the Tayside Clinical Trials Unit (TCTU) and hosted by HIC, to preserve allocation concealment. The TRuST system will be based on the study protocol; system validation and User Acceptance Testing will follow HIC and TASC SOPs; CI review and approval will be carried out prior to the live system release.

The study arms are:

- Continue oral iron
- Stop oral iron
- Stop oral iron and give IV iron (as per local formulary).

Direct care physicians (i.e. GP or hospital clinician) will receive written notification of the randomisation allocation. Participants will be verbally informed of treatment allocation (telephone visit). Treatment allocation will be recorded in the participant medical record.

Where web-access is not possible at site, emergency randomisation will be provided by TCTU via [contact]; following the TCTU Unblinding Work Instruction. Verbal notification of randomisation will be provided; email record of emergency randomisation will be provided when web-access is available) and filed in the participant medical record.

A minimisation algorithm with a random element will be used to ensure balance across recruitment centres and key baseline measures. Randomisation will be stratified by site, and further balanced using minimisation. Haemoglobin after minimum 8 weeks of oral iron (>=100g/L vs <100g/L), ferritin prior to commencement of oral iron (>=50ug/L vs <50ug/L) and six minute walk distance (>=300m vs <300m) will be the minimisation variables.

Only those involved with development and maintenance of the system will have access to the treatment allocations during the study; those involved with outcome assessment or statistical analysis will not have access to allocation until the point of the final analysis after database lock. Unblinding will occur following OC database lock; the CI will formally request unblinding.

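### Criterion 9 is not written as an alternative to criterion 7, so relapsed patients are wholly or partly excluded, and their minimisation haemoglobin is ambiguous

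*Protocol*

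**What the plan says.** Protocol section 4.2 opens the inclusion list with the rule that a participant "must meet all of the following criteria".

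- **Criterion 7** is "Insufficient response to oral iron therapy (sufficient response defined as improvement in Hb of 20g/L after a minimum of 8 weeks of oral iron therapy", with a second limb: Hb above the lower limit of normal for sex also counts as sufficient.
- **Criterion 9** is introduced by the closing words of "deemed not appropriate by the treating clinician. Only if applicable" and reads "Oral iron therapy provided an initial sufficient response however Hb has now fallen below lower limit of normal for sex". Its bracket repeats the same two limbs and the same 8-week minimum as criterion 7.

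Section 4.2 also sets a pre-iron Hb of 85 to 110 g/L. Section 7.1.1 lists the results needed for eligibility: Hb and ferritin before oral iron, and one Hb after at least 8 weeks of it, with no date limit. It adds that the Hb drawn at Visit 1 is not needed to decide eligibility.

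Section 5.5.1 names three minimisation variables. One is "Haemoglobin after minimum 8 weeks of oral iron (>=100g/L vs <100g/L"). It does not say which on-treatment result to enter if there are several.

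The Scientific Summary (S.2) has a different definition: "sufficient response defined as improvement in Hb by 20g/L within 3 months of commencement of oral iron therapy". It has no limb for the lower limit of normal.

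**The concern.** Criterion 9 has only one evident purpose: to let in people who responded at first and then relapsed. Yet it sits in a list that must be met in full, beside a criterion that asks for the opposite response under the same definition. The qualifier before it makes criterion 9 conditional. It does not switch criterion 7 off.

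This matters more here than in most trials because the pilot measures recruitment. The monthly randomisation rate is co-primary (section 2.2.1). Eligible patients per site, and the proportion who agree and pass screening, are secondary outcomes (section 2.2.2). The four sites were chosen to see whether the recruitment methods work in different regions (section 5.1.1). If sites read the criteria differently, that could look like a difference between sites, and the mix of never-responders and relapsed patients could vary as well.

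There is little room for informal repair. Section 5.4 rules out rescreening, and section 14.2 says that protocol waivers will not be approved.

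The undated Hb raises a smaller question for the same patients: which value goes into the minimisation.

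**Working it through.** The plan states no figure to reproduce on this point. The check is one of logic, with simple arithmetic.

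**Inputs.** Pre-iron Hb 85 to 110 g/L, response threshold +20 g/L or above the lower limit of normal (LLN) (section 4.2); minimisation cut 100 g/L (section 5.5.1). Section 4.2 gives no figure for the LLN and local laboratory ranges apply. *Assumption:* 120 g/L for women and 130 g/L for men, from the WHO definition cited in S.2, with 115 to 125 and 125 to 135 as the range.

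**Step 1: criterion 7 read as never having had a sufficient response.** Criterion 9 requires a past sufficient response under the same definition. The two are complementary, so no relapsed patient meets both, whatever the LLN.

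**Step 2: criterion 7 judged on current Hb.** A relapsed patient now below the LLN fails criterion 7 when

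pre-iron Hb + 20 ≤ current Hb < LLN.

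| Patient (LLN 120) | Pre-iron | Peak | Now | Rise now | Criterion 9 | Criterion 7 |
|---|---|---|---|---|---|---|
| A | 100 | 125 | 105 | 5 | met | met |
| B | 88 | 125 | 110 | 22 | met | not met |

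The failing region exists whenever pre-iron Hb + 20 < LLN. That is pre-iron Hb below 100 at an LLN of 120, and below 110 at 130. Across the LLN range the bound is 95 to 105 for women. For men it runs from 105 up to 115, which covers the whole permitted range.

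Enumerating integer values (peak up to 160, current from 70) shows the same pattern:

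| LLN | Relapsed combinations | Meet 7 on Step 1 reading | Meet 7 on Step 2 reading | Fail 7 on Step 2 reading |
|---|---|---|---|---|
| 120 | 58,120 | 0 | 52,640 | 5,480 |
| 130 | 64,935 | 0 | 52,260 | 12,675 |

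These are counts of grid cells, not of patients, and are not prevalences.

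**Step 3: minimisation stratum.** The lowest Hb that counts as a sufficient response is 85 + 20 = 105 g/L; the LLN limb gives a higher value at every LLN tried. Since 105 > 100, entering the response value puts every relapsed patient in the upper stratum. A patient with pre-iron 90, peak 121 and now 95 would be placed at ≥100 although the current value is below 100. Entering the current value gives no such error. The wording of section 5.5.1 fits either.

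**Step 4: the two response definitions.** A woman who goes from 110 to 122 has a rise of 12 g/L. That is insufficient under S.2 but sufficient under section 4.2 (122 > 120). A rise of 20 g/L first reached in month 4 also divides them: too late for S.2, sufficient under 4.2, which has no upper time limit.

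**The case against.** A reader might infer that criteria 7 and 9 can never both be met, or that the whole list cannot be satisfied. The documents do not support either. Criterion 9 is conditional, so ordinary non-responders qualify on criteria 1 to 8. Criterion 7 does not say that the patient must never have responded, and criterion 9 itself contrasts an initial response with the Hb now. On the current-Hb reading many relapsed patients meet both, as patient A shows. The qualifier may also be meant as a sub-heading that sets criterion 9 apart, and its purpose is easy to guess.

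It can also be said that divergence between sites is not demonstrated. A medically qualified person confirms every criterion (section 5.3). Sites have initiation training and an Operations Manual (sections 7.1 and 12.2), and screening logs with reasons for ineligibility go to the trial manager monthly. That is fair: differing readings are possible, not shown, and the logs might reveal them.

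On minimisation, a reader might infer that balance on current Hb is bound to fail. It fails only if the older value is entered. Even then one of three minimisation factors is affected, allocation stays valid, and the Hb and ferritin analyses adjust for baseline level and site (section 9.2).

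On the S.2 wording, section 4.2 is the operative text and S.2 is a summary, so that mismatch is minor.

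What stands is that neither reading of criterion 7 admits everyone whom criterion 9 describes. Only an either/or rule does, and the protocol does not state one.

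**Conclusion.** The point holds as a drafting defect confined to relapsed patients. They are all excluded if criterion 7 means never having responded. If it is judged on current Hb, those still at least 20 g/L above their pre-iron value are excluded. The second result needs an LLN more than 20 g/L above the pre-iron Hb, which occurs at every LLN tried. The first needs no assumption.

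The protocol does not say how many relapsed patients to expect, so the effect on eligible counts, the randomisation rate and case-mix cannot be calculated. It could be negligible if such patients are rare. The minimisation ambiguity is the lesser part: misclassification of current Hb is possible, not certain, and touches balance only. The case for acting is that the rule works against its own purpose in a trial whose outcomes are recruitment counts, and that the correction is nearly free.

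**What to change.** 1. Reword section 4.2 so that a participant must meet criteria 1 to 6 and 8, plus either 7 or, where applicable, 9.
2. Record the entry path on the CRF. Because a relapsed patient can meet both criteria on current Hb, the item should capture whether a sufficient response was ever documented.
3. Define the Hb used for criterion 7, for the present-state part of criterion 9 and for minimisation as the most recent result before randomisation after at least 8 weeks of oral iron. Put the same wording in sections 4.2, 5.5.1 and 7.1.1, and say whether the Visit 1 result counts if it is already back.
4. Reconcile the response definition in S.2 with that in section 4.2.

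The cost is a wording amendment, one CRF item and a clearer label for one randomisation input. The sample size does not change. It is not necessary to delete criterion 9, which would drop a group that the protocol evidently means to admit. Nor need every randomisation wait for the Visit 1 Hb: section 7.1.1 uses Visit 1 results for eligibility only as a fallback for creatinine and eGFR.

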#### 4.3 EXCLUSION CRITERIA

To be eligible, the participant will be assessed, and none of the following criteria will be present:

- 1. Active GI cancers
- 2. Active (unhealed) peptic ulcer disease
- 3. No ferritin level performed prior to commencing oral iron
- 4. Bleeding disorders
- 5. Taking oral anticoagulants (antiplatelet agents are permitted)
- 6. Weight loss of >5Kg in the last 3 months (as a possible marker of occult cancer)
- 7. Estimated GFR of <30ml/min/1.73m^2 by CKD-EPI equation

- 8. Symptomatic chronic heart failure (NYHA (21) class III and IV); note asymptomatic left ventricular systolic or diastolic dysfunction is not classed as heart failure; the use of heart failure medications are permitted
- 9. Terminal illness with life expectancy less than 3 months as deemed by the local investigator
- 10. Severe cognitive impairment precluding written informed consent
- 11. Unable to mobilise without human assistance (walking aids are allowed)
- 12. Previous reaction to intravenous iron
- 13. Participating in another clinical trial (other than observational trials and registries) concurrently or within 30 days prior to screening for entry into this study.

#### 5 PARTICIPANT SELECTION AND ENROLEMENT

#### 5.1 IDENTIFYING PARTICIPANTS

#### 5.1.1 Study sites

Participants will be recruited from four UK NHS sites: Grampian, Fife, Norfolk & Norwich, and Newcastle. The sites are selected as one large and one smaller site in both Scotland and England to establish the recruitment plan for the main study and to test whether these methods work in different geographical regions; for the main we anticipate increasing the number of sites, depending on the required sample size.

#### 5.1.2 Channels of recruitment

Recruitment will target participants living in the community; in their own or another person's home, sheltered housing and care home (i.e. not in hospital). Recruitment will target the following channels:

- Hospital clinics
- GP practice lists
- Laboratory results lists
- Research volunteer databases, including SHARE.

Recruitment strategies include (1) primary and secondary care oral iron prescriptions, (2) NHS electronic haematology records, (3) NHS clinicians and GPs identification of their patient lists (acute, outpatient and GP databases), (4) press release with associated recruitment materials such as posters displayed in hospital and GP surgeries (5) research volunteer database searches. Details are provided below (section 5.1.3).

Implementation will be through appropriate Research Ethics Committee, Caldicott Guardian and NHS R&D (22) consultants and GPs. For volunteers who contact directly to research team, we will check with their medical records regarding eligibility after their consent.

#### 5.1.3 Recruitment Strategies

#### (i) Primary and secondary care prescriptions

To identify potentially eligible participants, oral iron prescription searches will be performed by Primary Care Network, GPs and/or hospital clinicians.

#### (ii) Laboratory results lists

To identify potentially eligible participants, biochemistry and haematology results listings will be created by the NHS laboratory at each site. Haemoglobin results will be reviewed by GPs/hospital clinicians or delegated.

#### (iii) Patient Lists

#### Hospital clinics

Potential participants will be identified by the clinical teams who look after the older patients (any speciality). Study protocol and eligibility criteria will be made known to all relevant clinical departments by the research team at participating sites; regular visits to these departments will be scheduled to ensure visibility and awareness of the study.

- Clinical teams will review patients receiving oral iron treatment to establish potential eligibility.
- The clinician will write to eligible participants using the Invitation Letter, providing the brief Participant Information Brochure, and inviting those interested in taking part to reply using the reply slip and stamped addressed envelope or to call or e-mail the study team.

#### **GP** Practice lists

Potential participants will be identified via the NHS Research Scotland Primary Care Network (NRSPCN) and NIHR Primary Care Network as follows:

• Research active general practices in the NRS / NIHR PCN will be invited to join the study.

Recruitment of patients from the primary care by NRS & NIHR Primary Care Network
 The NRSPCN (previously called SPCRN) / NIHRPCN will be involved in recruitment of patients
 to this study from primary care. Network staff provide GP practices with an expert service to

undertake searches of their electronic databases to identify potentially eligible patients and prepare the ethically approved letters to be sent out by the practice. Network staff work on behalf of the healthcare team under practice staff supervision. Each member of Network staff must have a current NHS substantive or honorary contract in order to carry out these activities. Searches are undertaken of each GP practice database and the list generated by the search is screened by a clinician before the letters are sent out on behalf of the practice. Patients are asked to contact the research team if they are interested in participating in the study.

- Using the practice IT system and the Community Health Index (CHI) number (a unique NHS Scotland patient identifier) / relevant identifier a search of patients receiving oral iron treatment will be carried out to establish potential eligibility will be carried out to identify potentially eligible participants;.
- The GP will write to eligible patients using the Invitation Letter, providing the brief Participant Information Brochure, and inviting those interested in taking part to reply using the reply slip and stamped addressed envelope or to call or e-mail the study team.

#### (iv) Press release and advertising

Press and advertising in appropriate health care setting advertising will be utilised. The Sponsor will approve press release and/or advertisements. Interested individuals will contact the research team to request study information.

